2.4 Secondary Endpoints

The secondary endpoints of this study are:

- Overall response rate in the subset of patients with measurable disease.
- Clinical benefit rate (Complete response (CR) + Partial response (PR) + Stable disease (SD) x 6 months).
- Duration of response (DOR).
- Percentage of patients progression-free at 4 and 6 months.
- Overall survival (OS).
- Safety and tolerability of everolimus with an anti-estrogen therapy.

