10.3 Analysis Population

The following analysis populations will be used:

- Efficacy Evaluable Population is defined as all patients who receive at least 1 cycle of study treatment and have at least one post-baseline assessment. (Patients who discontinue treatment during Cycle 1 will not be replaced in the study.)
- Safety Population is defined as all patients who have received any dose of study treatment.

CONFIDENTIAL

STUDY DRUG(S): EVEROLIMUS
FINAL PROTOCOL DATE: 19 JUNE 2014

SCRI INNOVATIONS STUDY NUMBER: BRE 212
VERSION 1.0

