10.4.2 Efficacy Analysis

All efficacy analyses will be performed using the Efficacy Evaluable Population.

- Overall Response Rate (ORR) is defined as the proportion of patients with observed complete response (CR) or partial response (PR) according to the RECIST v1.1 criteria.
- Clinical Benefit Rate (CBR) is defined as the proportion of patients with CR, PR or SD x 6 months according to the RECIST v1.1 criteria.
 - For ORR and CBR, patients without a post-baseline tumor assessment will be classed as not evaluable (NE) and considered as non-responder.
- Progression Free Survival (PFS), defined as the time from the first day of study drug administration (Day 1) to disease progression (event) as defined by the RECIST v1.1 criteria, or death (event) on study. Patients who are alive and free from disease progression will be censored at the date of last tumor assessment. Patients who receive non-protocol therapy (subsequent therapy) prior to incurring an event will be censored at the date of last tumor assessment prior to the start of subsequent therapy. Patients who do not have a post-baseline tumor assessment will be censored at the date of first treatment (Day 1).
- Overall Survival (OS), defined as the time from the first day of study drug administration (Day 1) or death on study. Patients who are alive will be censored at the date of last known date alive.
- Duration of Response (DOR), is defined as the time from the first date of CR or PR to disease progression or death as defined by the RECIST v1.1 criteria. Patients who are alive and free from disease progression will be censored at the date of last tumor

CONFIDENTIAL

STUDY DRUG(S): EVEROLIMUS
FINAL PROTOCOL DATE: 19 JUNE 2014

SCRI INNOVATIONS STUDY NUMBER: BRE 212
VERSION 1.0

assessment. Patients who receive non-protocol therapy (subsequent therapy) prior to incurring an event will be censored at the date of last tumor assessment prior to the start of subsequent therapy. Only those patients who achieved CR or PR will be included in the summaries of DOR.

- Percentage of patients progression-free at 4 and 6 months, defined as the proportion of patients who are progression-free as defined by the RECIST v1.1 starting from the date of their first treatment.

For ORR and CBR, the estimates and the associated 95% CI (based on both asymptotic normal approximation and exact binomial methods) will be calculated.

Best overall response will be tabulated: CR, PR, SD, PD and not evaluable (NE).

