1.2 Study Design	
Study Type	 Non-Randomized  Randomized (Allocation Ratio:)
Details	
This is a multi-centered, open-labeled, Phase II study in MBC. The patient population includes locally recurrent or MBC patients with cytologically or histologically confirmed hormone receptor-positive breast cancer who have demonstrated disease progression on prior anti-estrogen therapy or therapies. Eligible patients must have evaluable or measurable disease per RECIST v1.1.
 
Progression Free Survival (PFS), defined as the time from the first day of study drug administration (Day 1) to disease progression (event) as defined by the RECIST v1.1 criteria, or death (event) on study. Patients who are alive and free from disease progression will be censored at the date of last tumor assessment. Patients who receive non-protocol therapy (subsequent therapy) prior to incurring an event will be censored at the date of last tumor assessment prior to the start of subsequent therapy. Patients who do not have a post-baseline tumor assessment will be censored at the date of first treatment (Day 1).
 
Overall Survival (OS), defined as the time from the first day of study drug administration (Day 1) or death on study. Patients who are alive will be censored at the date of last known date alive.
 
Duration of Response (DOR), is defined as the time from the first date of CR or PR to disease progression or death as defined by the RECIST v1.1 criteria. Patients who are alive and free from disease progression will be censored at the date of last tumor assessment. Patients who receive non-protocol therapy (subsequent therapy) prior to incurring an event will be censored at the date of last tumor assessment prior to the start of subsequent therapy. Only those patients who achieved CR or PR will be included in the summaries of DOR.
 
PFS (efficacy primary endpoint), OS and DOR (efficacy secondary endpoints) estimates will be generated using Kaplan-Meier methods, both for all patients enrolled and those patients receiving the MTD. Four month and six month PFS estimates with 95% confidence intervals (CIs), and median PFS and OS with 95% CIs, will be calculated.
 
Best overall response will be tabulated: CR, PR, SD, PD and not evaluable (NE).
 
Overall Response Rate (ORR) is defined as the proportion of patients with observed complete response (CR) or partial response (PR) according to the RECIST v1.1 criteria.
 
Clinical Benefit Rate (CBR) is defined as the proportion of patients with CR, PR or SD x 6 months according to the RECIST v1.1 criteria.
 
For ORR and CBR, patients without a post-baseline tumor assessment will be classed as not evaluable (NE) and considered as non-responder.

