Table 5	Treatment and Dose Modifications	Duration on Treatment (weeks), N, Mean, SD, Median, Min, Max Dose Reduction (n, %) None Patients with 1 Patients with 2 Patients with >= 3 Dose Interruption (n, %) None Patients with 1 Patients with 2 Patients with >= 3	Safety
Table 6	Measurable Lesions	Measurable Lesions (n, %) Non-Measurable Lesions (n, %) Evaluable Bone Only Disease (n, %)	Enrolled Patients
Table 7	Best Overall Response	Best overall response (n, %): Complete response (CR), Partial response (PR), Stable disease (SD), NonCR/NonPD, Progressive disease (PD), Not evaluable (NE), Not applicable (N/A) Missing Objective Response Rate (ORR) (= CR+PR): ORR, 95% Confidence interval Clopper-Pearson	Efficacy Evaluable, Safety

Standard TFLs			
Table No	Description	Variables/Analyses To Be Included	Population
		Normal Approximation Clinical Benefit Rate (CBR) $(=CR+PR+SD \geq 4 \text{ months})$: CBR, 95% Confidence interval Clopper-Pearson Normal Approximation Clinical Benefit Rate (CBR) $(=CR+PR+SD \geq 6 \text{ months})$: CBR, 95% Confidence interval Clopper-Pearson Normal Approximation]	
Table 8	Progression-free Survival (Kaplan-Meier estimates & 95% CI)	Number of patients with events, Number of patients censored, Median Progression-free Survival [months (95% CI)] 25% Percentile Follow-up [months (95% CI)] 75% Percentile Follow-up [months (95% CI)] Progression-free Survival Estimates [probability, (95% CI)]: 4 months, 6 months, 12 months	Efficacy Evaluable, Safety
Table 9	Overall Survival (Kaplan-Meier estimates & 95% CI)	Number of patients with events, Number of patients censored, Median Overall Survival [months (95% CI)] 25% Percentile Follow-up [months (95% CI)] 75% Percentile Follow-up [months (95% CI)] Overall Survival Estimates [probability, (95% CI)]: 4 months, 6 months, 12 months	Efficacy Evaluable, Safety
Table 10	Adverse Event Overview	Any Adverse Event Treatment-related Adverse Event Everolimus-related Adverse Event Anti-Estrogen Therapy-related Adverse Event Serious Adverse Event Treatment-related Serious Adverse Event Serious Adverse Event leading to Death Treatment-related Serious Adverse Event leading to Death Adverse Events leading to Treatment Discontinuation Adverse Events leading to Treatment Interruption Adverse Events leading to Treatment Reduced	Safety

Standard TFLs			
Table No	Description	Variables/Analyses To Be Included	Population

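### ORR is defined in patients with measurable disease, but the analysis text assigns it to populations that can include bone-only patients, who cannot reach partial response

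*Protocol*

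**What the plan says.** Protocol 2.4 lists the endpoint as "Overall response rate in the subset of patients with measurable disease".

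The analysis text differs:

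- **Protocol 10.4.2:** "All efficacy analyses will be performed using the Efficacy Evaluable Population". ORR is then defined as a proportion of patients, with no condition on measurable disease. The one patient-handling rule for ORR keeps people in the denominator: "patients without a post-baseline tumor assessment will be classed as not evaluable (NE) and considered as non-responder".
- **Protocol 10.3:** "Efficacy Evaluable Population is defined as all patients who receive at least 1 cycle of study treatment and have at least one post-baseline assessment", and "Safety Population is defined as all patients who have received any dose of study treatment". Neither definition mentions measurable disease, and SAP section 2 uses the same two definitions.
- **SAP 1.2:** repeats the unrestricted definition and names no population for ORR.
- **SAP section 4, endpoint table:** groups ORR with OS, DOR and CBR, with Efficacy Evaluable as the primary analysis population and Safety as the other.
- **SAP Table 7:** reports best overall response, ORR and CBR in both populations.

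Inclusion criterion 7 (Protocol 3.1) admits patients with lytic or mixed bone lesions and no measurable disease. SAP Table 6 has a row that counts bone-only patients.

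**The concern.** The endpoint in 2.4 and the quantity in SAP Table 7 have different denominators. The difference is not neutral, because the extra patients cannot respond in the usual way. Without measurable lesions a patient has no target lesions, and Appendix E defines partial response through target lesions. Only complete disappearance of non-target disease could make a bone-only patient a responder.

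The ORR in Table 7 would then depend partly on how many bone-only patients were enrolled, as well as on activity in measurable disease. It would not be comparable with an ORR reported in measurable disease elsewhere. Two competent programmers could produce different values, each defensible from the documents. If the choice is left until the data are in, it can be made with the results in view.

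**Working it through.** **Who can respond under Appendix E**

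1. Target lesions are chosen from measurable lesions, so a bone-only patient has none.
2. Partial response is at least a 30% fall in the summed target-lesion diameters. Every row of the overall-response table that yields PR needs a target-lesion response of CR or PR.
3. Non-target disease can be classed only as CR, SD or PD. A bone-only patient can therefore reach CR but not PR.

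**Does any rule remove these patients from the ORR denominator?** I looked in Protocol 10.3 and 10.4.2, SAP 1.2, SAP section 2, the SAP endpoint table and SAP Tables 6 and 7, and found none. By contrast, both documents do state a subset for DOR, restricting it to responders.

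**Size.** The documents give no ORR target, bone-only share or bone-only CR rate, so there is no figure of theirs to reproduce and all three inputs are assumptions. Let f be the bone-only share, p the ORR in measurable disease and c the CR rate in bone-only patients.

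Reported ORR = (1 − f)p + fc, so reported ORR − p = −f(p − c).

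With p = 20%:

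| c | f = 10% | f = 20% | f = 30% | f = 40% |
|---|---|---|---|---|
| 0% | 18.0% | 16.0% | 14.0% | 12.0% |
| 5% | 18.5% | 17.0% | 15.5% | 14.0% |
| 10% | 19.0% | 18.0% | 17.0% | 16.0% |
| 20% | 20.0% | 20.0% | 20.0% | 20.0% |

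For example, f = 30% and c = 5% gives 0.70 × 20% + 0.30 × 5% = 15.5%. With c = 0 and f = 20/30/40%, p = 10% is reported as 8/7/6% and p = 30% as 24/21/18%.

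**In patients.** The denominator of 42 is the planned evaluable number in Protocol 10.2. Intervals are Clopper-Pearson 95%, and no bone-only patient has a CR.

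| Bone-only | ORR in measurable disease | ORR over all 42 |
|---|---|---|
| 4 (9.5%) | 8/38 = 21.1% (9.6–37.3) | 8/42 = 19.0% (8.6–34.1) |
| 8 (19.0%) | 7/34 = 20.6% (8.7–37.9) | 7/42 = 16.7% (7.0–31.4) |
| 13 (31.0%) | 6/29 = 20.7% (8.0–39.7) | 6/42 = 14.3% (5.4–28.5) |
| 17 (40.5%) | 5/25 = 20.0% (6.8–40.7) | 5/42 = 11.9% (4.0–25.6) |

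With 13 bone-only patients and one bone-only CR, the right-hand figure becomes 7/42 = 16.7% (7.0–31.4).

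**Minor, CBR in Table 7.** The shell lists NonCR/NonPD apart from SD and adds a Not applicable row; neither label is defined. Appendix E calls persisting non-target disease SD, and under that label no bone-only patient is lost from CBR. The worst case requires every bone-only patient to be labelled NonCR/NonPD and none counted. With exponential PFS and a 5-month median, the loss is then f × 0.5^(6/5) = 0.435f, or 8.7, 13.1 and 17.4 points at f = 20%, 30% and 40%. Table 7 also shows CBR with a 4-month threshold beside the 6-month one, whereas the definitions in both documents use 6 months only.

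**The case against.** The strongest reply is that 2.4 governs. It defines the endpoint, while 10.4.2 only names the analysis set, so ORR could be taken in the measurable subset of that set without contradiction. The rows for bone-only disease in Table 6 and for NonCR/NonPD and Not applicable in Table 7 suggest that the authors had patients without target lesions in mind. That is a sensible way to reconcile the texts, but no analysis rule or table shell says so, and the tables will be programmed from the SAP. The Not applicable row would not settle it even if meant for these patients, since being listed there does not take a patient out of the denominator.

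Several narrower points do stand:

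- ORR is secondary and descriptive, with no target, test or decision rule attached.
- The size rests wholly on assumptions. With only 4 bone-only patients among 42, the gap is about 2 points and the intervals are nearly the same.
- The CBR worst case is a hypothetical mislabelling. The defined 6-month CBR is present in Table 7, so the 4-month row needs at most a label.
- An ORR over all evaluable patients is a legitimate summary. Amending 2.4 would also remove the contradiction.

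**Conclusion.** The inconsistency is real. SAP Table 7 as written gives an ORR over a different denominator from the endpoint in Protocol 2.4. The reported value is lower whenever the CR rate in bone-only patients is below the ORR in measurable disease, by f(p − c). At an assumed p of 20% and c of zero this is 2 to 8 percentage points for bone-only shares of 10% to 40%; at c = p it is nil. The intervals overlap throughout, so the objection is to what is being estimated rather than to a demonstrable shift in the result.

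The primary PFS analysis and the sample size are untouched, and DOR already has its own responder subset. This should be corrected before analysis, but it does not threaten the main conclusion of the trial. The CBR points are minor.

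**What to change.** In Protocol 10.4.2, SAP 1.2, the SAP endpoint table and SAP Table 7, state that the ORR denominator is patients with measurable disease at baseline, within Efficacy Evaluable and, for the supporting analysis, within Safety. An ORR over all patients in each population can be shown beside it under its own label. If the sponsor prefers the wider denominator for the endpoint itself, 2.4 must be amended to say so before the data are analysed.

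Use the baseline classification behind SAP Table 6, with two precautions. That table counts enrolled patients, so the denominator must be recounted within each analysis population. The shell also does not say that its rows are mutually exclusive, so the measurable-disease flag needs an explicit definition.

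Also state that NonCR/NonPD lasting at least 6 months counts as SD in CBR, consistent with Appendix E; define Not applicable; and mark the 4-month CBR as additional.

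The cost is wording and one filter on data already planned; nothing new is collected. The price is precision: in the example with 13 bone-only patients, the interval is 39.7 − 8.0 = 31.7 points wide at n = 29, against 28.5 − 5.4 = 23.1 at n = 42.

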2.5 Exploratory Objectives

The exploratory objective of this study is:

- To evaluate the VeriStrat assay in this HR-positive patient population treated with everolimus in combination with anti-estrogen therapy.

3. STUDY PATIENT POPULATION AND DISCONTINUATION

3.1 Inclusion Criteria

Patients must meet all of the following criteria in order to be included in the research study:

1. Histologic diagnosis of unresectable, locally recurrent or MBC.
2. ER and/or PR-positive tumors with staining by immunohistochemistry (IHC) based on the most recent biopsy.
3. Only 1 previous chemotherapy regimen for MBC. Patients progressing while receiving adjuvant endocrine therapy or progressing <12 months from completion of adjuvant endocrine therapy are eligible.

CONFIDENTIAL

STUDY DRUG(S): EVEROLIMUS
FINAL PROTOCOL DATE: 19 JUNE 2014

SCRI INNOVATIONS STUDY NUMBER: BRE 212
VERSION 1.0

4. Progressed on anti-estrogen therapy (tamoxifen, fulvestrant, anastrozole, letrozole, exemestane, toremifene, or LHRH agonists in conjunction with anti-estrogen therapy) defined as:

- Recurrence while on, or within 12 months of end of anti-estrogen therapy for early stage breast cancer, or
- Progression while on, or within one month of anti-estrogen therapy for locally advanced or metastatic breast cancer.

Note: No washout for anti-estrogen therapy required.

Anti-estrogen therapy does not have to be the last treatment prior to study entry.

5. Post- menopausal or pre/peri-menopausal women on tamoxifen. LHRH agonists may be used to render ovarian suppression with postmenopausal ranges of estradiol or FSH per institutional guidelines.

6. HER2-negative breast cancer, defined as follows:

- Fluorescent In Situ Hybridization (FISH)-negative (FISH ratio <2.0), or
- IHC 0-1+, or
- IHC 2-3+ AND FISH-negative (FISH ratio <2.0).

7. Measureable disease as measured by Response Evaluation Criteria in Solid Tumors (RECIST) criteria version 1.1 (See Appendix E) or evaluable bone lesions, lytic or mixed, in absence of measureable disease by RECIST criteria.

8. Adequate hematologic function, defined by:

- Absolute neutrophil count (ANC) $\geq 1.5 \times 10^9/L$
- Platelet count $\geq 100 \times 10^9/L$
- Hemoglobin $>9 \text{ g/dL}$.

9. Adequate liver function, defined by:

- Aspartate aminotransferase (AST) and alanine aminotransferase (ALT) $\leq 2.5 \times$ the upper limit of normal (ULN) or $\leq 5 \times$ ULN in presence of liver metastases)
- Total bilirubin $\leq 1.5 \times$ ULN.

10. Adequate renal function, defined by:

- Serum creatinine $\leq 1.5 \times$ ULN or calculated creatinine clearance of $\geq 40 \text{ ml/min}$.

CONFIDENTIAL

STUDY DRUG(S): EVEROLIMUS
FINAL PROTOCOL DATE: 19 JUNE 2014

SCRI INNOVATIONS STUDY NUMBER: BRE 212
VERSION 1.0

11. International normalized ratio (INR) ≤ 1.5 or prothrombin time (PT)/partial thromboplastin time (PTT) within normal limits (WNL) of the institution (if patient is not on anti-coagulation therapy).

Note: Patients receiving anti-coagulation treatment with an agent such as warfarin or heparin are eligible if the INR is stable and within the therapeutic range prior to first dose of everolimus.

12. Adequate lipid profile, defined by:

- Fasting serum cholesterol ≤ 300 mg/dL OR ≤ 7.75 mmol/L, AND
- Fasting triglyceride $\leq 2.5 \times$ ULN.

Note: In case one or both of these thresholds are exceeded, the patient can only be included after initiation of appropriate lipid lowering medication.

13. Age ≥ 18 years.

14. ECOG Performance Status score of 0-2 (See Appendix A).

15. Life expectancy of ≥ 12 weeks.

16. Willingness and ability to comply with study and follow-up procedures.

17. Ability to understand the nature of this study and give written informed consent.

3.2 Exclusion Criteria

Patients who meet any of the following criteria will be excluded from study entry:

1. Previous therapy or known intolerance/hypersensitivity with any approved or investigational mTOR inhibitor (e.g., temsirolimus, everolimus, sirolimus).
2. Patients who are ≤ 21 days after their most recent chemotherapy and have not recovered from side effects.
3. Use of an investigational drug ≤ 21 days or 5 half-lives (whichever is shorter) prior to the first dose of everolimus. For investigational drugs for which 5 half-lives is ≤ 21 days, a minimum of 10 days between termination of the investigational drug and administration of everolimus is required.
4. Wide field radiotherapy (including therapeutic radioisotopes such as strontium 89) administered ≤ 28 days or limited field radiation for palliation ≤ 7 days for metastatic disease prior to first dose of everolimus or has not recovered from side effects of such therapy.

CONFIDENTIAL

STUDY DRUG(S): EVEROLIMUS
FINAL PROTOCOL DATE: 19 JUNE 2014

SCRI INNOVATIONS STUDY NUMBER: BRE 212
VERSION 1.0

5. Previously untreated brain metastases. Patients who have received radiation or surgery for brain metastases are eligible if there is no evidence of central nervous system (CNS) disease progression, and at least 2 weeks have elapsed since treatment. Patients are not permitted to receive enzyme inducing anti-epileptic drugs (EIAEDs) during the study and should not be receiving chronic corticosteroid therapy for CNS metastases.
6. Cardiac disease, including: congestive heart failure (CHF) > Class II per New York Heart Association (NYHA, Appendix B) classification; unstable angina (anginal symptoms at rest) or new-onset angina (i.e., began within the last 3 months), or myocardial infarction within the past 6 months; symptomatic CHF, unstable angina pectoris, or cardiac ventricular arrhythmias requiring anti-arrhythmic therapy.
7. Patients who have any severe and/or uncontrolled medical conditions or other conditions that could affect their participation such as:
 - Severe impaired lung functions as defined as spirometry and diffusing capacity of the lung for carbon monoxide (DLCO) that is 50% of the normal predicted value and/or O₂ saturation that is 88% or less at rest on room air
 - Uncontrolled diabetes as defined by HbA1c >8% despite adequate therapy.
 - Liver disease such as cirrhosis or severe hepatic impairment (Child-Pugh class C)
 - Any history of a bleeding diathesis.
8. Impairment of gastrointestinal function or gastrointestinal (GI) disease that may significantly alter absorption of everolimus (e.g., ulcerative disease, uncontrolled nausea, vomiting, diarrhea, malabsorption syndrome, or small bowel resection).
9. Patients with known active hepatitis B (HBV) or hepatitis C (HCV) infection. Patients with risk factors for hepatitis (See Section 7.1) must have HBV DNA and HCV RNA testing by PCR, and are ineligible if these tests are positive.
10. Concurrent use of strong CYP3A4 inhibitors or inducers from 72 hours prior to initiation of study treatment until the end of treatment with everolimus (See Section 5.5).
11. Chronic treatment with systemic steroids or other immunosuppressive agents. Note: Topical or inhaled corticosteroids are allowed.
12. Patients receiving immunization with attenuated live vaccines within 1 week of study entry or during study period (See Section 5.4).

CONFIDENTIAL

STUDY DRUG(S): EVEROLIMUS
FINAL PROTOCOL DATE: 19 JUNE 2014

SCRI INNOVATIONS STUDY NUMBER: BRE 212
VERSION 1.0

13. Pregnant or lactating women or women of childbearing potential without a negative serum pregnancy test, ≤ 7 days prior to date of first treatment, regardless of the method of contraception used.
14. Patients with known human immunodeficiency virus (HIV) seropositivity.
15. History of other malignancy ≤ 5 years of study entry which could affect compliance with the protocol or interpretation of results. Note: History of curatively treated basal or squamous cell carcinoma of the skin or in situ carcinoma of the cervix, or ductal carcinoma in situ (DCIS) of the breast treated with lumpectomy alone with curative intent, are generally eligible.
16. Significant concurrent, uncontrolled medical condition which, in the opinion of the investigator, may interfere with patient participation in the study.

